6.2. Data and Safety Monitoring Plan

Ongoing trial oversight is carried out by the principal investigator, [name] and the primary research nurse. These individuals will meet regularly to review recently acquired data, and adverse events. Institutional support of trial monitoring is provided in accordance with the FHCRC Institutional Data and Safety Monitoring Plan. Under the provisions of this plan, the FHCRC research Trials Office coordinates monitoring of data accuracy and compliance by consultants, contract research organizations, or FHCRC employees unaffiliated with the conduct of the study. Independent monitoring visits occur at specified intervals determined by the assessed risk level of the study and the findings of previous visits. In addition, protocols are reviewed at least annually by the Protocol and Data Monitoring Committee (PDMC) and the Institutional Review Board (IRB). The PDMC reviews accrual, adverse events, stopping criteria, and adherence to the data and safety monitoring plan. The PHCRC IRB reviews the study progress and safety information to assess continued acceptability of the risk-benefit ratio for human subjects. Approval of both committees is necessary to continue the study.

7. Statistical Considerations

A maximum of 25 patients will be entered. Stopping earlier would happen under 2 circumstances:

- 1.) Excess probability that patients have to be admitted to hospital during the 4-7 days of outpatient chemotherapy.
- 2.) Excess probability that patients die during the 14 days after beginning outpatient treatment.

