For both 1 and 2 the case for stopping will be evaluated using the program "predictive probabilities" freely available from the Statistics Department at MD Anderson Cancer Center (<https://biostatistics.mdanderson.org/softwaredownload/>). In particular stopping will occur based on the Bayesian inequality probability $\Pr[\pi_i > \pi_j] > 0.90$ where \Pr = probability, π_i is the posterior probability for rate of admission to the hospital with current management and π_j the probability of rate of admission with former management. We will assume that π is distributed $\beta(a,b)$ where "a" is the number of successes (no admission) and "b" the number of failures (admission) with management approach i (current) or management approach j (previous). We will assume a prior of $\beta[25,25]$ for the previous approach corresponding to a 50% need for hospital admission with prior outpatient management in 50 patients and a prior of $\beta(5,1)$ with the current approach corresponding to our data indicating that 5 patients have been treated as outpatients without need for inpatient admission while 1 has been admitted. As patients up to a maximum of 25 are entered on the current approach its prior will be updated and compared to the $\beta[25,25]$ distribution using the inequality probability 0.90 noted above. With this configuration here are the predictive probabilities that the current approach (called A) is truly better than the previous approach $\beta[25,25]$ denoted B given various numbers of successes (no admission during days 4-7) and failures (admission).

Successes (No admission)	Failures (Admission)	Predictive Probability A (current) better than B (Previous)
1	0	0.95
0	1	0.74
0	2	0.51
0	3	0.31
0	4	0.16
0	5	0.07
1	6	0.05
1	5	0.12
2	6	0.09
3	6	0.15
3	7	0.06

We would stop accrual should the predictive probability be < 0.10 , for example in the 3 success / 7 failure scenario noted above. In this case 7 patients of 10 patients would have been admitted contrasted with the maximum acceptable rate of 4 admitted / 6 not.

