For the death within 14 days endpoint our prior for the current (inpatient) approach will be $\beta[49, 1]$ corresponding to a 2% (1/50) death rate and will be $\beta[5, 0]$ for the outpatient approach, corresponding to 0 deaths in the 5 patients who would have met eligibility criteria for the proposed protocol. These data will be updated as patients (up to the maximum of 25) are enrolled and the resultant beta distribution compared to the $\beta[49, 1]$ distribution noted above, using the inequality probability 0.9 noted in the section on admission to the hospital. With this configuration here are the predictive probabilities that the current approach (called A) is truly worse than the previous approach $\beta[49, 1]$ denoted B given various numbers of successes (no deaths days 1- 14) and failures (deaths days 1- 14).

Success (No death within 14 days)	Failure (death within 14 days)	Predictive Probability A (current) worse than B (Previous)
1	0	0.05
0	1	0.28
0	2	0.97
1	2	0.95
4	2	0.90
5	2	0.88
21	3	0.99

We would stop accrual should the predictive probability be > 0.90 , for example in cases where there are 2 failures and < 5 successes, or in any case where there are 3 deaths.

8. References

1. Moroney SD. Understanding Health Care Cost Drivers. National Institute of Health Policy. 2003.

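### Section 7: the outpatient death prior beta[5,0] is not a proper distribution and does not yield the printed table or the written stop at 2 deaths with 4 survivors; the 0.28 after a first-patient death is a separate error

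*Combined protocol and SAP*

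**What the plan says.** Section 7 (Statistical Considerations) monitors two endpoints with a predictive probability program, up to the planned total: "A maximum of 25 patients will be entered".

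For death within 14 days, the comparator is beta[49,1]. The outpatient prior "will be $\beta[5, 0]$ for the outpatient approach", and its basis is given as "corresponding to 0 deaths in the 5 patients who would have met eligibility criteria for the proposed protocol". The prior is updated as patients enrol and compared with beta[49,1] "using the inequality probability 0.9 noted in the section on admission to the hospital". A seven-row table follows, presented as the result of this configuration. It shows the predictive probability that the outpatient approach is worse:

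| Survivors / deaths | Printed |
|---|---|
| 1 / 0 | 0.05 |
| 0 / 1 | 0.28 |
| 0 / 2 | 0.97 |
| 1 / 2 | 0.95 |
| 4 / 2 | 0.90 |
| 5 / 2 | 0.88 |
| 21 / 3 | 0.99 |

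Accrual stops when this probability is above 0.90, "for example in cases where there are 2 failures and < 5 successes", and whenever there are 3 deaths. The action at 2 deaths and 4 survivors is therefore explicit: stop.

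**The concern.** A beta distribution with a second parameter of zero does not exist as a proper prior. Taken as a limit, it says that death is impossible until one is observed. With no deaths, the predictive probability of ending up worse than beta[49,1] must then be exactly zero, yet the first row prints 0.05. Some other prior must have been run, and the plan does not say which.

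The row for a first-patient death also looks out of place. One death and no survivors is printed at 0.28, and the next row, two deaths and no survivors, at 0.97.

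Section 2 calls mortality the more important of the two feasibility criteria. If the prior, the table and the written boundary do not agree, someone who reruns the rule as written could act differently from someone who reads the boundary in the text. Monitors who consult the table after an early death would also see a misleading figure.

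**Working it through.** **Inputs (all from Section 7).** Outpatient prior beta(5, x) on survival, with x = 0 as stated; comparator beta(49,1), held fixed; maximum N = 25; inner inequality threshold 0.90; stop if the predictive probability exceeds 0.90.

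**Method.** After s survivors and d deaths, the outpatient posterior is beta(a, b) with a = 5 + s and b = x + d. Because the comparator is beta(49,1),

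Pr(outpatient worse) = 1 − B(a + 49, b) / B(a, b), where B is the beta function.

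With m = 25 − s − d patients still to come, the chance of k further deaths is

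C(m, k) × B(a + m − k, b + k) / B(a, b).

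The predictive probability is the sum of these chances over every k for which the final Pr(outpatient worse) exceeds 0.90.

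**Check of the method on the plan's own figures.** The same calculation for admission, beta(5,1) against beta(25,25), gives the following in printed order:

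- Computed: 0.954, 0.739, 0.515, 0.310, 0.161, 0.071, 0.052, 0.125, 0.093, 0.150, 0.064
- Printed: 0.95, 0.74, 0.51, 0.31, 0.16, 0.07, 0.05, 0.12, 0.09, 0.15, 0.06

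All 11 rows agree within 0.006, so this is the method the plan used.

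**How many deaths in 25 count as worse under beta(5,0).**

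- 2 deaths: 1 − (28 × 29)/(77 × 78) = 1 − 812/6006 = 0.865, below 0.90.
- 3 deaths: 1 − (27 × 28 × 29)/(76 × 77 × 78) = 1 − 21924/456456 = 0.952, above 0.90.

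So at least 3 deaths among the 25 are needed. Once 3 have occurred, every completion qualifies and the predictive probability is 1.00.

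**Row 1/0.** The posterior is beta(6,0), which has all its mass on survival. The predictive probability is 0.00; printed 0.05.

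**Row 0/1.** The posterior is beta(5,1), with 24 patients to come and at least 2 more deaths needed.

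- No further death: 5/29 = 0.1724
- One further death: 24 × 5/(28 × 29) = 120/812 = 0.1478
- Predictive probability: 1 − 0.1724 − 0.1478 = 0.680; printed 0.28

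A larger x shifts the posterior towards death and can only lower the number of deaths needed, so the value rises with x. No x of zero or more gives less than 0.68.

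**Two deaths, s survivors.** At least one more death is needed, so the predictive probability is 1 − (5 + s)(6 + s)/812.

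| Survivors | Calculation | Result | Printed |
|---|---|---|---|
| 0 | 1 − 30/812 | 0.963 | 0.97 |
| 1 | 1 − 42/812 | 0.948 | 0.95 |
| 2 | 1 − 56/812 | 0.931 | – |
| 3 | 1 − 72/812 | 0.911 | – |
| 4 | 1 − 90/812 | **0.889** | 0.90 |
| 5 | 1 − 110/812 | 0.865 | 0.88 |

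Under the stated prior, two deaths stop accrual with up to 3 survivors, not 4.

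**Sensitivity to the second parameter x.**

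| x | 1/0 | 0/1 | 0/2 | 1/2 | 4/2 | 5/2 | 21/3 |
|---|---|---|---|---|---|---|---|
| Printed | 0.05 | 0.28 | 0.97 | 0.95 | 0.90 | 0.88 | 0.99 |
| 0 | 0.00 | 0.680 | 0.963 | 0.948 | 0.889 | 0.865 | 1.00 |
| 0.087 | 0.045 | 0.712 | 0.968 | 0.954 | 0.8987 | 0.875 | 1.00 |
| 0.1 | 0.052 | 0.717 | 0.968 | 0.955 | 0.9000 | 0.877 | 1.00 |
| 0.102 | 0.053 | 0.717 | 0.968 | 0.955 | 0.9002 | 0.877 | 1.00 |
| 0.3 | 0.160 | 0.778 | 0.976 | 0.966 | 0.918 | 0.898 | 1.00 |
| 0.5 | 0.378 | 0.924 | 1.00 | 1.00 | 1.00 | 1.00 | 1.00 |

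- Values of x from about 0.087 to 0.102 match five rows (1/0, 0/2, 1/2, 4/2, 5/2) to two decimals. None matches 0/1.
- Cell 4/2 crosses 0.90 at x = 0.0999.
- At x = 0.31, 2 deaths in 25 give a final inequality probability of 0.9001 (0.8996 at 0.305). From there on, two deaths stop accrual with any number of survivors.
- At x = 0.1 the complement of row 0/1 is 1 − 0.717 = 0.283. This would fit a one-cell slip, but the documents do not establish the cause.

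**The case against.** The strongest reply is that beta[5,0] is shorthand. Section 7 describes the parameters as counts of successes and failures, and five patients with no deaths gives 5 and 0. The program was probably run with a small positive value: at 0.1, five of the seven rows come out as printed and 4/2 just reaches 0.90. On that view the fault is an undisclosed input, not an unsupported boundary.

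The practical effect is also small. The boundary is written in counts, so monitors can apply it without knowing the prior. If outcomes are assessed one patient at a time, the disputed cell is reached only when the second death is the sixth patient. That has probability 5p²(1 − p)⁴, about 0.2% at a death rate p of 2%, 0.4% at 3% and 1.0% at 5%. Row 0/1 triggers no stop at 0.28, 0.68 or 0.72. The trial is a pilot that disclaims hypothesis testing.

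Most of this stands, and it limits the weight of the point. It does not remove it. The value 0.1 appears nowhere in the documents. The range that matches the table, 0.087 to 0.102, straddles the crossing at 0.0999, so the table cannot show whether 4/2 was above or below the cut-off. And no prior of this form explains 0.28.

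A second reply is that Section 7 also says "stopping will occur based on the Bayesian inequality probability" above 0.90, which could mean a plain posterior comparison without prediction. Under beta(5,0) that gives 1 − 110/(59 × 60) = 0.969 for 5/2, against 0.88 printed. It would also stop after a first-patient death (1 − 5/54 = 0.907) and at 2 deaths with up to 17 survivors (1 − 506/5112 = 0.901). That contradicts both the table and the written boundary, so it does not rescue them.

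**Conclusion.** The point holds. The stated prior is not proper and cannot have produced the first row (0.00 against 0.05). It contradicts the written boundary in one cell, 2 deaths and 4 survivors (0.889 against a stop above 0.90). Row 0/1 is wrong by a wide margin, 0.28 against 0.68 under the stated prior or 0.71 to 0.72 under the inferred one, and changing the second parameter does not repair it.

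The consequences are limited. One decision cell is affected, and the 3-death stop gives 1.00 for every prior tried. The other differences are within 0.02 and change no action.

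It should nevertheless be fixed, because the replacement prior has to be chosen and the boundary is sensitive to it. The written two-death rule follows from the model only for a second parameter between about 0.100 and 0.31. A conventional-looking 0.5 would give 0.924, and hence a stop, after a death in the first patient alone. The printed table rules out 0.5 as the prior originally run, but nothing in the text would prevent its use in a rerun.

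The conclusion assumes the predictive probability method with N = 25 and inner threshold 0.90, which the admission table confirms. The value near 0.1 is a back-calculation, and the complement explanation for 0.28 is unproven.

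**What to change.** In the death paragraph of Section 7:

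1. State the proper outpatient prior that was actually run, with both parameters above zero.
2. Regenerate all seven rows from it. Row 0/1 becomes about 0.72 if the prior is near beta(5, 0.1); other priors give other values.
3. Reconcile prior, table and written boundary at 2 deaths and 4 survivors. Show that cell to at least three decimals, since 0.90 printed against a rule of above 0.90 does not settle the action.

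Optionally, reword the general description of the method so that 0.90 is clearly the inner inequality threshold and stopping rests on the predictive probability, as the tables already imply.

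The cost is one rerun of a seven-row table and an edit to one paragraph. There is no operational cost.

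### Section 7 leaves two 0.90 stopping statements for 14-day death unreconciled, and its death table does not follow from the stated beta[5,0] prior

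*Combined protocol and SAP*

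**What the plan says.** Section 7 (Statistical Considerations) covers hospital admission and death within 14 days, with at most 25 patients. For both it names a program for predictive probabilities, and then says "In particular stopping will occur based on the Bayesian inequality probability" exceeding 0.90.

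For death, the comparator is beta[49,1] and the outpatient prior is beta[5,0], the latter "corresponding to 0 deaths in the 5 patients who would have met eligibility criteria for the proposed protocol". The updated distribution is to be compared with beta[49,1] "using the inequality probability 0.9 noted in the section on admission to the hospital". The table is introduced with "here are the predictive probabilities that the current approach (called A) is truly worse than the previous approach", and its column is headed as a predictive probability. The section closes with "We would stop accrual should the predictive probability be" above 0.90. Its examples are 2 deaths with fewer than 5 survivors, or any 3 deaths. The summary in Section 2 mentions only the 3 deaths.

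For admission, pi for the current approach "is the posterior probability for rate of admission to the hospital with current management", yet in the beta(a,b) given for pi the first parameter "is the number of successes (no admission) and" the second counts admissions.

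**The concern.** The posterior inequality asks how likely it is, on today's data, that outpatient treatment is worse. The predictive probability asks how likely it is that a criterion will be met once all 25 patients are in. With few events early in the trial the two can differ widely. Section 7 attaches 0.90 to both and never says how they relate. Describing the tabulated value as the chance that A is truly worse adds to the confusion, because those words describe the posterior.

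Section 2 calls treatment-related mortality the more important of the two feasibility criteria, and Section 6.2 has a monitoring committee review the stopping criteria. People outside the study team may therefore have to apply this text. Someone who recomputes the table from the stated prior will not recover it, and someone who computes the inequality can reach a different decision from the printed examples.

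**Working it through.** **Inputs (Section 7).** Maximum n = 25. Death: outpatient survival A ~ beta(5 + survivors, 0 + deaths), inpatient survival B ~ beta(49,1). Admission: A ~ beta(5 + not admitted, 1 + admitted), B ~ beta(25,25). Cutoff 0.90.

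**Step 1: reproduce the admission table.** Take the predictive probability as the beta-binomial chance, over the remaining patients, that Pr(A better) exceeds 0.90 at n = 25. All 11 printed rows match within 0.005; for example, 3 not admitted/7 admitted gives 0.064 (printed 0.06). The posterior there is 0.50, so the table is not the posterior. At n = 25, Pr(A better) is 0.904 with 15 not admitted and 0.844 with 14. At most 10 of 25 may therefore be admitted, which is the 4 in 10 of "contrasted with the maximum acceptable rate of 4 admitted / 6 not". The nested reading fits throughout.

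**Step 2: posterior inequality for death.** With A ~ beta(a,b), Pr(A worse) = 1 − E[A^49].
- 1 death in the first patient, beta(5,1): 1 − 5/54 = 0.907.
- 2 deaths in n patients, beta(a,2) with a = n + 3: 1 − a(a+1)/[(a+49)(a+50)].
- At n = 25: 2 deaths give 1 − 812/6006 = 0.865; 3 deaths give 1 − 21924/456456 = 0.952. The end-of-study criterion is therefore 3 deaths in 25.

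**Step 3: predictive probability for death under beta[5,0].** With 2 deaths already seen, at least one more is needed: 1 − a(a+1)/(28 × 29) = 1 − a(a+1)/812.

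| 2 deaths, n | Posterior inequality | Predictive |
|---|---|---|
| 5 | 0.978 | 0.911 |
| 6 | 0.974 | 0.889 |
| 7 | 0.969 | 0.865 |
| 10 | 0.953 | 0.776 |
| 15 | 0.925 | 0.579 |
| 19 | 0.901 | 0.377 |
| 20 | 0.895 | 0.320 |

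The two fall on opposite sides of 0.90 at n = 6 to 19. With 1 death in the first patient, at least two more are needed among 24: 1 − 5/29 − (24 × 5)/812 = 0.680, against a posterior of 0.907. Measured against the printed count boundary instead, the inequality disagrees with 2 deaths at n = 7 to 19 and with 1 death at n = 1. With 3 deaths both rules stop at every n.

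**Step 4: the death table.**

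| Survivors/deaths | Printed | Predictive, beta[5,0] | Posterior, beta[5,0] |
|---|---|---|---|
| 1/0 | 0.05 | 0 | 0 |
| 0/1 | 0.28 | 0.680 | 0.907 |
| 0/2 | 0.97 | 0.963 | 0.990 |
| 1/2 | 0.95 | 0.948 | 0.986 |
| 4/2 | 0.90 | 0.889 | 0.974 |
| 5/2 | 0.88 | 0.865 | 0.969 |
| 21/3 | 0.99 | 1.000 | 0.955 |

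At 1/0 the stated prior becomes beta[6,0], a point mass at no deaths, so the value must be 0. At 4/2 the value is 1 − 90/812 = 0.889, below the cutoff, although the text counts 2 deaths with fewer than 5 survivors as a stop.

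**Step 5: what might have been used (inference).** An outpatient prior of beta(5,0.1) gives 0.052, 0.717, 0.968, 0.955, 0.90001, 0.877 and 1.000. That fits every row within 0.01 except 0/1, where the printed 0.28 equals 1 − 0.717 after rounding and so looks like a complement.

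**The case against.** The strongest reply is that the working rule is plain enough. The named program, both column headings and both closing sentences point to the predictive probability, and the death boundary is given in counts. Since 5/2 is printed as 0.88 and 0/1 as 0.28, both below the cutoff, and more survivors only lower the value, a user can decide at every count without recalculating. Anyone who computes 0.97 at 5/2 would see that it does not match the printed 0.88. This is also a pilot that disclaims hypothesis testing. Most of this stands.

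A reader might therefore infer too much from the two sentences. One such inference is that the plan has no usable death boundary; the worked examples supply one. Another is that the table cannot be reproduced at all. Under beta[5,0], five of seven rows are within 2 points, and 4/2 is the only one of those five where the gap changes the decision. The beta(5,0.1) prior and the complement explanation are reverse-engineered and prove nothing about what was run.

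What the reply does not remove is that the nested reading has to be recovered by calculation, that it departs from the literal inequality sentence, and that even under it the stated prior does not give the death table.

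**Conclusion.** The point holds as an internal inconsistency and a reproducibility fault. Two 0.90 statements are left unreconciled. Under the stated priors they differ with 2 deaths at n = 6 to 19 and with 1 death at n = 1. Three table rows are off in a way that matters: 1/0 and 0/1 in value, and 4/2 in which side of 0.90 it falls.

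The conflict range depends on the prior: under the assumed beta(5,0.1) the inequality stays above 0.90 with 2 deaths up to n = 21, and with 1 death at n = 1 and 2.

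For scale, assume every outcome is known at each look; Section 7 gives no look schedule. At the 3% death rate that Section 3.1 ties to eligibility, the chance of stopping is 4.5% under the printed boundary and 13% under the inequality with a look after every patient, or 4.2% and 8.5% with looks every 5 patients. These differences arise only if someone applies the inequality at interim looks, which the worked examples make unlikely. The documents do not support a claim that the printed boundary is itself wrong.

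**What to change.** In Section 7:
- State for each endpoint which quantity governs stopping. If it is the predictive probability, say that the 0.90 inequality is the criterion applied at n = 25.
- Relabel both table columns as the predictive probability of meeting that criterion at n = 25.
- State the proper outpatient prior actually used for death and recompute the table from it. Correct 1/0 and 0/1 as needed, and show 4/2 to enough decimals to place it relative to 0.90.
- Align the count examples, and the short summary in Section 2, with the result.
- Define pi consistently as either an admission rate or a no-admission rate, so that the direction of the inequality is fixed.

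The cost is wording and one recomputed table. The printed boundary need not change if the predictive rule and the prior that produced the table are confirmed. If the inequality is chosen instead, the plan should report the higher chance of stopping: at a true 2% death rate it rises from 1.7% to 7.0% with a look after every patient, or from 1.6% to 4.0% with looks every 5 patients.

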- 2.) $<5\%$ of patients die within 14 days of beginning outpatient chemotherapy.

2. Background and Study Rationale

Medical practice over the past 20 years has tried to curb health care costs by increasing outpatient treatment and care for common medical procedures in patients with mainstream conditions. An example of this would be the establishing of "day surgical procedure units". Little focus has been on the "outlier healthcare consumer", those patients that make up a fraction of the population, but disproportionately consume resources¹. Those patients can drive up healthcare cost with a rare, life threatening disease.

Little research has been done to look at the health care economics of acute myeloid leukemia (AML). Commonly today, acute myeloid leukemia (AML) is treated with induction and consolidation chemotherapy in an inpatient hospital setting. Feasibility of outpatient consolidation chemotherapy has been examined², but induction chemotherapy to induce remission in an outpatient setting has not been done.

Research has shown that it is not the LOS (length of stay) fueling the cost of hospital admissions, but front loaded costs; the cost that occur during the "early stage of admission when resource consumption is most intense"³. We have already shown that patients can be safely early discharged once induction therapy is complete. This can be done without an increase in "treatment-related mortality" (TRM) provided the patients are doing well at discharge, live in proximity to UW/SCCA, have an outpatient caregiver, and are committed to return for outpatient follow-up⁴. While we have not quantified the effects of early discharge on cost or quality-of-life, it seems likely that these effects are favorable. We have also shown that, regardless of neutrophil count, patients can be discharged from the hospital after successful treatment of "neutropenic fever" without increase in mortality or admission to the ICU⁵. We have addressed patient safety and early discharge and now want to look one step further. We want to go beyond cost containment of early stage hospital admission and take a look at the feasibility of moving induction chemotherapy for AML patients to an outpatient treatment setting.

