This protocol is an extension of our early discharge experience. Specifically it will examine the feasibility of administering to selected outpatients an induction chemotherapy regimen that would usually be administered to inpatients, as will still be the case for most patients. Although administration of the regimen requires only 4-7 days, there could be great cost savings per patient multiplied by many patients and the same seems highly plausible as applied to a patients' quality-of-life.

We will use 2 criteria to assess “feasibility”. The first is whether an excessively high proportion of patients need to be admitted to hospital during administration of chemotherapy because of complications such as vomiting, infection etc. The need to admit a high proportion of patients would at the very least increase work required by providers. Our unpublished experience with outpatient induction is that 15% of a series of 13 patients with relapse were admitted prior to completion of therapy. We propose these data as our historical control, but any specific number will be arbitrary. Certainly the relevance and utility of outpatient therapy would be in doubt were the proportion much above 50%, so we have chosen this number. The 2nd and more important criterion is TRM attributable to administration of typically inpatient chemotherapy to outpatients. “Attributable” is also somewhat nebulous but TRM within 14 days of beginning chemotherapy seems reasonable. Current TRM rates for patients receiving chemotherapy as inpatients are <5%⁶. Hence it would require many patients given chemotherapy as outpatients to be confident that the outpatient TRM rate is similarly low. Such hypothesis testing is not our intent. We merely intend to enter a maximum of 25 patients stopping early should it become likely that our 2 criteria for feasibility will not be met. Our statistical section (see section 7.0) provides the rationale supporting our stopping rules, briefly stated that the study if 7 of 10 patients are hospitalized, or if 3 patients die.

3. Eligibility

Our eligibility requirements have been selected to minimize the chance of TRM and, probably, the need for admission to hospital during the days of chemotherapy administration.

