3.1. Inclusion Criteria

- 1.) Signed Written Informed Consent a.)
The signed informed consent.
b.) The benefits / risks of the induction chemotherapy regimen will be reviewed, and a second consent may be necessary if the regimen will be administered according to a separate protocol.
- 2.) AML (APL excepted) or high-risk MDS (10-19% blasts in marrow by morphology or flow cytometry or blood).
- 3.) Meet the eligibility criteria for the selected inpatient protocol that they will receive as an outpatient.

To receive the treatment as an outpatient they must:

- a.) Treatment-related mortality (TRM) score (ref) <9.21 corresponding to a TRM rate of 3% when chemotherapy of similar intensity as proposed here is administered to inpatients.
- b.) Ages ≥ 18 years of age
- c.) Blast count $\leq 10,000$
- d.) Fibrinogen > 200
- e.) Afebrile with clear chest imaging and no signs of active viral, bacterial, fungal infection unless determined to be, at the discretion of the investigator, not clinically significant in the context of this study.
- f.) Adequate cardiac function as demonstrated by LVEF of 45% or greater, by MUGA or echocardiogram. No ongoing cardiac issues such as uncontrolled arrhythmias or unstable angina or congestive heart failure.
- g.) Patient must have an outpatient caregiver available.

- h.) Patient must live within 30 minutes of the treating physician's office during outpatient treatment.
- i.) Patient must be willing to return to the treating physician's office for outpatient follow-up once outpatient treatment is completed.
- j.) Logistical requirements:
 1. Space available in infusion room.
 2. Outpatient infusion pump available if continuous infusion required.
 3. Case discussed with infusion room nursing staff.

Note: age and white blood count are already components of the TRM score, but are included here for safety purposes

4. Treatment Plan

- 1.) Patients will be treated according to the operative inpatient induction chemotherapy regimen for which they will also provide informed consent.
- 2.) Treatment must begin on Monday, Tuesday, Wednesday, Thursday, or Friday after discussion with the 5th floor Infusion Room staff.
- 3.) If treatment includes ara-C at a daily dose of $\geq 1\text{g/m}^2$ patients will receive steroid eye drops and prednisone 100 mg daily or its IV equivalent.
- 4.) Patients must be followed daily during administration of chemotherapy. Evaluation will be until completion of chemotherapy.

Evaluation will include:

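### The 14-day death stopping rule in Section 7 cannot be fully reproduced from its stated prior, is described in three different ways, and is not tied to the <5% criterion (minor)

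*Combined protocol and SAP*

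**What the plan says.** Section 1 (Objectives, item 2) sets the criterion that fewer than 5% "of patients die within 14 days of beginning outpatient chemotherapy". Section 2 says "The 2nd and more important criterion is TRM" and describes a trial of at most 25 patients, "stopping early should it become likely that our 2 criteria for feasibility will not be met". It also says of confidence in a low death rate that "Such hypothesis testing is not our intent". Its summary of the rule is to stop "the study if 7 of 10 patients are hospitalized, or if 3 patients die".

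Section 7 opens with "For both 1 and 2 the case for stopping will be evaluated using the program", naming a predictive-probability program. It then says that stopping is based on a posterior inequality exceeding 0.90. For deaths, the comparator is beta(49,1), a 2% death rate, and the outpatient prior is beta(5,0), from 0 deaths in 5 patients. A seven-row table follows. The operative sentence stops accrual when the predictive probability is above 0.90, with the examples of two deaths and fewer than five survivors, "or in any case where there are 3 deaths".

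Section 3.1 limits entry to a risk score "corresponding to a TRM rate of 3" per cent in inpatients.

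**The concern.** Three things do not fit together.

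- **The table and the prior.** Some rows of the death table, including the one that sets the two-death cut-off, do not follow from the prior printed above it. A monitor who recomputes the rule would get a different cut-off.
- **Three descriptions of one rule.** The posterior inequality, the predictive probability and the Section 2 summary lead to different actions after the same deaths.
- **The rule and the criterion.** In at most 25 patients a second death fixes the final observed rate at 2/25 = 8% or more, while 1/25 = 4% is the most that <5% allows. The rule is anchored at 2% and continues after a second death once five patients have survived. That sits uneasily with the stated purpose of stopping when a criterion is likely to be missed.

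At stake is whether the safety rule can be applied and audited as written, and whether a trial finishing with two deaths has a clear reading on its more important criterion.

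**Working it through.** Notation: s/d means s survivors and d deaths. All inputs are from Section 7: maximum 25 patients, comparator beta(49,1), outpatient prior beta(5,0), and cut-offs of 0.90 for the inequality and for the predictive probability.

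**1. Which quantity is tabulated.** Take the predictive probability as the beta-binomial chance, over the patients still to come, that the posterior inequality exceeds 0.90 at n=25. Applied to the admission table, with beta(5,1) against beta(25,25), this reproduces all 11 printed rows within 0.01. The interim inequality does not: at 3 successes and 7 failures the posterior is beta(8,8), symmetric like beta(25,25), so the inequality is 0.50, against the printed 0.06. The tables are therefore predictive probabilities evaluated at n=25.

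**2. What is flagged at n=25.** For outpatient survival X ~ beta(5+s, d), Pr(worse) = 1 − E[X^49].

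- 2 deaths: 1 − (28×29)/(77×78) = 1 − 812/6,006 = 0.865
- 3 deaths: 1 − (27×28×29)/(76×77×78) = 1 − 21,924/456,456 = 0.952

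Only three or more deaths clear 0.90, so the predictive probability is the chance of reaching three deaths by patient 25.

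**3. The death table.** After two deaths it equals 1 − (5+s)(6+s)/812. For 0/1, the chance of no further death is 5/29 = 0.172 and of exactly one is 24×5/812 = 0.148, so the result is 1 − 0.172 − 0.148 = 0.680. For 1/0, a zero second parameter leaves no chance of death, so the result is 0.00.

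| s/d | Printed | beta(5,0) | beta(5,0.1), assumed |
|---|---|---|---|
| 1/0 | 0.05 | 0.00 | 0.052 |
| 0/1 | 0.28 | 0.680 | 0.717 |
| 0/2 | 0.97 | 1 − 30/812 = 0.963 | 0.968 |
| 1/2 | 0.95 | 1 − 42/812 = 0.948 | 0.955 |
| 4/2 | 0.90 | 1 − 90/812 = 0.889 | 0.90001 |
| 5/2 | 0.88 | 1 − 110/812 = 0.865 | 0.877 |
| 21/3 | 0.99 | 1.00 | 1.00 |

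Under beta(5,0), 3/2 gives 1 − 72/812 = 0.911 and 4/2 gives 0.889. The stated threshold therefore implies two deaths with fewer than four survivors. The last column is only a guess at what was run; that prior is not in the documents. It fits every row within 0.01 except 0/1, whose printed 0.28 is 1 − 0.717 after rounding.

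**4. Effect on stopping.** Assume independent deaths at a constant rate p, each outcome known before the next entry, and ignore the admission rule. The printed boundary stops with probability Pr(3 or more of 25) + 15p²(1−p)^23, where 15 counts the placements of two deaths in the first six patients. At p = 3% this is 3.8% + 15×0.0009×0.496 = 4.5%. The fewer-than-four version loses 5p²(1−p)^23 = 0.2 points, giving 4.2%. At 2%, 4% and 5% the pairs are 1.7 and 1.6%, 8.6 and 8.3%, 13.9 and 13.5%.

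**5. The inequality applied literally at interim.** For a second death at patient n it is 1 − (n+3)(n+4)/[(n+52)(n+53)].

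- n=7: 1 − 110/3,540 = 0.969
- n=19: 1 − 506/5,112 = 0.901
- n=20: 1 − 552/5,256 = 0.895

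It would stop for a second death at patients 7 to 19, where the printed rule continues.

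**6. Finishing with 2/25.** Of the 300 placements of two deaths, 15 stop the trial, so the chance is 285p²(1−p)^23.

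- p = 3%: 285×0.0009×0.496 = 12.7%
- p = 5%: 285×0.0025×0.307 = 21.9%
- p = 2% and 4%: 7.2% and 17.8%

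**The case against.** A stopping limit is not a success criterion. Section 7 compares outpatients with a 2% comparator and is nowhere given the task of forcing the final proportion below 5%. Section 2 disclaims hypothesis testing. If <5% means the underlying rate, 2/25 does not settle it: the exact 95% interval is 1.0% to 26.0%, and continuing is then not inconsistent. At true rates of 2% to 4% the criterion is met in truth, so finishing with two deaths there is no failure of the rule. All of this stands, and it confines the third part of the point to the observed-proportion reading.

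On the table, the five rows with two or three deaths agree within 0.02, the three-death clause is exact, and the 0/1 and 1/0 rows cannot trigger stopping under any of these values. A reader might infer that the whole table is wrong, especially from the interim inequality (0.974 at 4/2); but that is not the quantity tabulated. What remains is one entry clearly wrong under the stated prior (0/1), one that cannot arise from it (1/0), and one that moves the cut-off (4/2).

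On the wording, Section 7 names the program and both operative sentences use the predictive probability, while Section 2 presents its version as a brief summary. The intent can be worked out, but no sentence says that the inequality applies at n=25. Committee review of the stopping criteria and expedited death reports reduce the safety risk; they do not settle which wording applies.

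**Conclusion.** The point holds and is minor. The death rule cannot be reproduced in full from its documented prior: the threshold implies fewer than four survivors where the text says fewer than five, and the 0/1 entry is 0.68 where 0.28 is printed. The change in stopping probability is at most 0.4 percentage points for true rates of 2% to 5%. The inequality, the predictive probability and the Section 2 summary are not the same rule. The rule permits completion at 8% observed deaths, so it does not by itself deliver the aim in Section 2 if <5% is an observed proportion.

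A reader might go further and infer that the boundary is too loose and should stop at any second death. The documents do not support that. Such a rule would stop 8.9%, 17.2% and 26.4% of trials at true rates of 2%, 3% and 4%, against 1.7%, 4.5% and 8.6% now, and two deaths in 25 do not show a true rate above 5%. Nor should the criterion be restated as fewer than 3 of 25: that would loosen <5% to <12% and turn a safety limit into a feasibility target.

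The conclusion rests on the predictive-probability reading, which the admission table supports, and on the simple model in step 4 of the working.

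**What to change.** Amend the text of Sections 2 and 7:

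1. State the outpatient prior actually used for deaths. Correct the 0/1 row and any other row that does not follow from it, and make the worded cut-off agree with the recomputed table.
2. If that is the intent, state that the predictive probability governs interim stopping and that the 0.90 inequality is evaluated at n=25.
3. Reconcile the Section 2 summary with Section 7, which also stops for two early deaths.
4. Keep <5% as the feasibility criterion and state that it is judged separately from the stopping limit, so that 2/25 observed deaths does not meet it as an observed proportion.

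The cost is a short amendment, with no extra patients and no change asked for in the stringency of the boundary. The downside is slightly less favourable wording for a trial that finishes with two deaths.
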